
3.1.1 Screening Phase

Potential subjects will be identified using the protocol inclusion and exclusion criteria. With their permission, subjects may be screened and recruited from Aim 1: Cardio risk factors in DS youth (IRB #12-009233), which is recruiting male and female subjects with Down syndrome in the age range of 10-20 years of age. Additional children will be recruited from local primary care pediatric practices and from the Division of Endocrinology where children with DS are routinely referred for thyroid function abnormalities. A telephone interview and medical record review to determine eligibility will be conducted on subjects who are not recruited from #9233.

3.1.2 Observation Phase

The first 6 months of the study are the Observation Phase of the study. Only subjects with persistently elevated TSH during the Observation Phase will proceed to the Treatment Phase. Subjects that have TSH >10 mIU/L during the 6 month Observational Phase will have a repeat TSH test within 1-2 weeks. If the repeat TSH is >10 mIU/mL, the subject not be considered to have subclinical hypothyroidism and will not qualify to continue the study. They will be referred to an endocrinologist for treatment. Subjects who have TSH <5 mIU/L at the 6 month visit may have a repeat TSH test within 1-2 weeks; this will be at the discretion of the study investigator. If TSH or repeat TSH (if applicable) is <5 mIU/L, the subject will be considered to have normal levels of TSH and will not qualify to continue the study. Subjects who have a history of subclinical hypothyroidism, but at the 0 month visit have a TSH value in the normal range, may have a repeat TSH test within 3-6 months; this will also be at the discretion of the study investigator.

Study Visit #1 (0 Month):- For subjects recruited from #9233, #9233 data will serve as Study Visit #1 data. Study visit #1 will not be necessary for subjects recruited from #9233.

Subjects who have not participated in Study #9233 will complete Study Visit #1. Subjects and their parents/guardians will come to the research facility following a 12 hour overnight fast. Parental/guardian/Legal Authorized Representative consent and child assent (if child is deemed capable of assent) will be obtained prior to any study procedures being performed. Females will receive a urine pregnancy test. Females found to be pregnant will be disqualified from the study and will receive appropriate counseling and referral. Study participants will have the following measures: fasting blood samples, TSH, T4, anthropometric measurements, whole body DXA scan, blood pressure, pubertal assessment, pulse wave velocity & pulse wave analysis, echocardiography and questionnaire assessments. After the study visit, subjects will be asked to wear a physical activity arm band at home for 7 days, and a 3 day dietary recall will be done by telephone.

Blood Draw Visit A(3 Month):- During this observation time frame, subjects will have a blood draw to check TSH and T4 levels. This blood draw can be done at the research facility or at other hospital-affiliated sites.

Study Visit #2 (6 Month): – Subjects and their parents/guardians will present to the research facility following an overnight fast. At this study visit, the subject will have the following measures: fasting blood samples, TSH, T4, anthropometric measurements, whole body DXA scan, blood pressure, pubertal assessment and questionnaire assessments. Females will receive a urine pregnancy test. Females found to be pregnant will be disqualified from the study and will receive appropriate counseling and referral. After the study visit, subjects will be asked to wear a physical activity arm band at home for 7 days, and a 3 day dietary recall will be done by telephone.

3.1.3 Treatment Phase

Randomization and blinding -

Only subjects with persistently elevated TSH (5 – 10 mIU/mL) will be randomized into the following 2 groups of 10: Group 1 (Delayed treatment) or Group 2 (Immediate treatment). A 3 month supply of placebo will be dispensed to subjects that have been randomized into Group 1 and a 3-month supply of levothyroxine will be dispensed to subjects randomized into Group 2.

Blood Draw Visit B (7.5 Month): TSH and T4 will be measured 6 weeks after the Study Visit #2 (approximately 7.5 months from the start of the study). Subjects will obtain a blood draw. Dose adjustments will be made for Group 2 as needed. Another 3-month supply of placebo or levothyroxine (dose adjusted as necessary) will be mailed to the home. Subjects requiring dose adjustments will have TSH and T4 in another 6 weeks to confirm/assure TSH is in the desired range.

Study Visit #3 (12 Month): – Subjects and their parents/guardians will present to the research facility following a 12-hour overnight fast. At this study visit, the subject will have the following measures: fasting blood samples, TSH, T4, anthropometric measurements, whole body DXA scan, blood pressure, pubertal assessment and questionnaire assessments. Females will receive a urine pregnancy test. Females found to be pregnant will be disqualified from the study and will receive appropriate counseling and referral. After the study visit, subjects will be asked to wear a physical activity arm band at home for 7 days, and a 3 day dietary recall will be done by telephone. TSH and T4 will be reviewed and levothyroxine will now be dispensed to both Groups 1 and 2. Group 2 will continue on current dose if TSH within range; otherwise dose adjustments will be made as necessary.

Blood Draw Visit C (13.5 Month): TSH and T4 will be measured 6 weeks after the 12 month visit (approximately 13.5 months from the start of the study). Subjects will have blood drawn. A subsequent blood draw 6 weeks later will be required for any dose adjustments.

Study Visit #4 (18 Month): – Subjects and their parents/guardians will present for a final follow up at research facility following a 12-hour overnight fast. At this study visit, the subject will have the following measures: fasting blood samples, TSH, T4, anthropometric measurements, whole body DXA scan, blood pressure, pubertal assessment and questionnaire assessments. Females will receive a urine pregnancy test. Females found to be pregnant will be disqualified from the study and will receive appropriate counseling and referral. After the study visit, subjects will be asked to wear a physical activity arm band at home for 7 days, and a 3 day dietary recall will be done by telephone.

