Non-HDL-C	X		X			X		X
HbA1C	X		X			X		X
PAI-1	X		X			X		X
Hs-CRP	X		X			X		X
IL-6	X		X			X		X
Adiponectin	X		X			X		X
Leptin	X		X			X		X
Lipoprotein subclass analysis	X		X			X		X
T4	X	X	X		X	X	X	X
TSH	X	X	X		X	X	X	X
ANTITPO		X						
ANTITG		X						
Physical activity armband (Worn for 7 days after study visit)	X		X			X		X
Randomization				X				

Dispense study medication (placebo or levothyroxine)				X				
Dispense levothyroxine – both groups						X		
Dietary intake	XXX		XXX			XXX		XXX
Drug Compliance					X	X	X	X
Adverse Events					X	X	X	X

FIGURE 1: STUDY DIAGRAM

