1.4 Selection of Drugs and Dosages

Levothyroxine (T4) is a synthetic form of thyroxine, an endogenous hormone secreted by the thyroid gland. T4 is converted to its active metabolite, L-triiodothyronine (T3). Thyroid hormones (T4 and T3) then bind to thyroid receptor proteins in the cell nucleus and exert metabolic effects through control of DNA transcription and protein synthesis. Thyroid hormones are involved in normal metabolism, growth, and development, promote gluconeogenesis, increase utilization and mobilization of glycogen stores, stimulate protein synthesis, and increase basal metabolic rate. Onset of action for the oral form of levothyroxine is 3-5 days. Oral tablets are available in a number of doses: 25 mcg, 50 mcg, 75 mcg, 88 mcg, 100 mcg, 112 mcg, 125 mcg, 137 mcg, 150 mcg, 175 mcg, 200 mcg, 300 mcg. In children, pills are frequently cut in half to further refine doses: 37.5 mcg, 44 mcg, 56 mcg, 62.5 mcg, 68.5 mcg. Younger children tend to require higher doses for body weight of thyroxine replacement than older children and adults with hypothyroidism (TSH >10 mIU/L).

Typical doses for individuals with hypothyroidism, based on age, are: age 6-12 year: 4-5 mcg/kg/day; age > 12 years: 2-3 mcg/kg/day; adults and in older children in whom growth is complete: 1.7 mcg/kg/day. For subclinical hypothyroidism, a starting dose of 0.5-1

mcg/kg/day is typical. For the purposes of this study, subjects will be initiated on a dose between 0.5-1 mcg/kg/day, depending on the available tablet formulations and the PI's medical discretion. TFTs will be checked 6 weeks after treatment initiation and titrated to achieve TSH 0.5-3 mIU/L range.

Generic lactase tablets will be used as placebo and will be dispensed by the CHOP Investigational Pharmacy.

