2.2 Secondary Aim

- 1) To explore the effect of levothyroxine replacement on small LDL-P, fat mass, BMI Z score, and inflammation in pre-adolescents and adolescents with subclinical hypothyroidism and DS. Hypothesis: We hypothesize thyroxine treatment of subclinical hypothyroidism will decrease small LDL-P, decrease fat mass, decrease BMI Z score, and decrease inflammation
 - 2) To determine the effect of levothyroxine replacement on QOL, lifestyle (physical activity, nutrition) and body image in pre-adolescents and adolescents with DS and subclinical hypothyroidism. Hypothesis: Treatment of subclinical hypothyroidism will be associated with improved QOL , physical activity, and body image in pre-adolescents and adolescents with DS and subclinical hypothyroidism.
-

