- ABAS-II – The Adaptive Behavior Assessment System-Second Edition is widely used to evaluate individuals with intellectual and developmental disabilities measuring daily living skills (what people actually do, or can do, without the assistance of others). It assesses adaptive behavior in individuals 5-21 years of age.
 - Body Satisfaction Scales – The body satisfaction scales measure the level of satisfaction with body size, shape and weight.
 - HFI – The Home Food Inventory is a valid assessment of the home food environment. Families will be mailed the HFI prior to the study appointment and will be asked to bring the completed survey to the study appointment.
 - Physical activity/armband diary – Participants will be asked to keep a record of the times that they did not wear the physical activity armband and of their activities on the days that they wore the armband. The diary packet will be sent home with each participant, along with a postage-paid envelope to return the diary.
 - Sense Wear® Armbands (Body Media, Inc): Participants will pick up the Sense Wear armbands at the visit. The subject will be asked to wear the armband accelerometer for 7 consecutive days, 24 hours per day. The exception of wearing the armband is when the subject is bathing/showering or if participating in water activities, such as swimming. Information collected will include the amount and intensity of physical/sedentary activities and sleep.
 - 3 day dietary recalls: After the study visit, a nutritionist will contact the participant and guardian by phone to collect information as to what the participant ate and drank within the last 24 hours. This will be done three times (2 weekdays and 1 weekday).

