The study team will review potential side effects and toxicities with subjects by telephone 4 weeks after treatment initiation. If symptoms are present, TSH and T4 will be checked and dose adjustments made if necessary. If symptoms are absent, TSH and T4 will be checked as scheduled and symptoms reviewed at 6 weeks. All symptoms will be recorded. The Investigative team will have immediate access to TSH and T4 when these data are available from the lab. Thyroid function data will also be reviewed monthly by the study team, to assess study dosing practice.

For subjects enrolled in this study, any subject who develops TSH > 10 mIU/L during the course of the study will have a repeat TSH test done within 1-2 weeks. If the repeat TSH remains > 10 mIU/mL, the subject will be withdrawn from the study and referred to endocrinology for management of hypothyroidism. If a suppressed TSH (TSH < 0.1 mIU/L) is identified in a child on placebo, the TSH will be repeated within 2-3 weeks. If the TSH remains suppressed the subject will be referred to endocrinology for management of possible hyperthyroidism. If a suppressed TSH (TSH < 0.1 mIU/L) is identified in a child on levothyroxine, the levothyroxine dose will be decreased and the lab repeated within 4-6 weeks. If the TSH remains suppressed or child has symptoms consistent with hyperthyroidism, the TSH will be discontinued and the TSH repeated in 6 weeks. If the TSH remains suppressed the subject will be referred to endocrinology for management of possible hyperthyroidism,

At the completion of the study, serum TSH and T4 will be measured, thyroid hormone replacement will be discontinued, and thyroid hormone results from the study reported to the PMD. The subject will be directed to follow-up with the primary care provider or with pediatric endocrinology to determine if continued thyroid hormone replacement is appropriate.

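### The month-12 armband week and diet recalls follow the visit at which Group 1 is given levothyroxine, so the placebo-controlled comparison on these two measures may be partly diluted

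*Combined protocol and SAP*

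**What the plan says.** Section 2.2 makes lifestyle part of the second secondary aim: "To determine the effect of levothyroxine replacement on QOL, lifestyle (physical activity, nutrition) and body image". Its hypothesis predicts improved physical activity.

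For Study Visit #3, Section 3.1.3 lists blood, DXA, anthropometry and questionnaires at the visit, and then: "After the study visit, subjects will be asked to wear a physical activity arm band at home for 7 days". The schedule table (Table 1) likewise puts the armband in the week after each study visit. For diet, Section 5.1 says: "After the study visit, a nutritionist will contact the participant and guardian by phone". Three calls are made, each covering the previous 24 hours, and no window in days is given.

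The same visit paragraph states: "TSH and T4 will be reviewed and levothyroxine will now be dispensed to both Groups 1 and 2". Table 1 marks the row "Dispense levothyroxine – both groups" in the month-12 column. Section 3.1 has levothyroxine initiated in Group 1 at month 12. Section 6.1.1 confines the cross-sectional, placebo-controlled comparison to the second 6-month period.

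On drug timing, Section 1.4 states: "Onset of action for the oral form of levothyroxine is 3-5 days". Section 9.4.2 gives 6 weeks as the time to steady state.

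**The concern.** Group 1 is on placebo only from month 6 to month 12, so month 12 is the one point at which untreated and treated children can be compared concurrently. Samples, scans and questionnaires are obtained at or before the visit and precede the switch. The armband record and the recalls do not. If Group 1 starts its new supply at about the visit, its end-of-placebo activity and diet are recorded during its first days on active drug.

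Any resulting bias runs toward no difference. It falls on the only device measure of activity and the only record of what the child ate and drank. With 10 children per arm there is little precision to spare, and on-drug days cannot be removed afterwards unless dose dates and measurement dates were recorded.

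**Working it through.** The plan gives no figure for this point, so there is none to reproduce. The check has two parts.

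**1. When does Group 1 start levothyroxine relative to the armband week?** No section states the day of first dose. Three provisions point to about the day of the visit:

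- Section 9.4.2 checks TSH and T4 6 weeks after levothyroxine initiation. Section 3.1.3 places Blood Draw Visit C 6 weeks after the month-12 visit. The two agree only if initiation falls at about the visit.
- Placebo is supplied as 3 months at randomization plus 3 months mailed after the month-7.5 draw: 3 + 3 = 6 months, covering months 6 to 12. Table 1 shows no placebo dispensed at month 12.
- Section 4.5 has families bring their bottles to Visit #3.

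No section tells Group 1 to stay on placebo until the armband week and recalls are complete.

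**2. How much exposure could fall in the armband week?**

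*Day count.* With a first dose on the visit day, all 7 armband days are on levothyroxine. With onset at 3–5 days, 7 − 5 = 2 to 7 − 3 = 4 days follow onset, which is 29% to 57% of the week. If the first dose comes after the week, the count is 0.

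*Accumulation.* Assume an exponential approach to steady state, with the 6 weeks (42 days) equal to 4 or 5 half-lives. The documents do not state a half-life.

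- Rate: k = ln 2 / (42/h), where h is the number of half-lives in 42 days.
- Fraction of steady state at day 7: 1 − exp(−7k).
- Mean fraction over days 0–7: 1 − [1 − exp(−7k)]/(7k).

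| h | half-life (days) | 7k | at day 7 | mean, days 0–7 |
|---|---|---|---|---|
| 4 | 10.5 | 0.462 | 0.37 | 0.20 |
| 5 | 8.4 | 0.578 | 0.44 | 0.24 |

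Taking h = 6 instead gives a mean of 0.28.

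*From exposure to contrast.* If activity tracked concurrent exposure with no lag, and both arms had the same steady state, the month-12 contrast would shrink by the mean fraction, 20–24%. The sample needed to keep the same power rises by 1/(1 − f)²: 1/0.80² = 1.56 and 1/0.76² = 1.73. These are ceilings under the 4–5 half-life assumption.

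*Recalls.* With no call window, the time on drug at each recall cannot be bounded.

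**Month 6.** The armband and recalls also follow Visit #2, and the month-7.5 draw is counted both from that visit (Section 3.1.3) and from the start of study drug (Section 3.1). Group 2's month-6 values could overlap with drug start in the same way.

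**The case against.** **Dispensing is not dosing.** The supply is released after TSH and T4 are reviewed, an earlier supply is mailed home, and the first-dose day is nowhere stated. A reader might infer that the documents fix the switch before the armband week. They do not, although part 1 of the working makes a start at about the visit the natural reading. What stands regardless is that the plan secures no placebo week for these measures.

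**The lifestyle aim is not lost.** A reader might conclude that it has no clean month-12 value. That goes too far. The ASAQ (sedentary time), CEBQ and CFQ are completed at the visit, and the HFI before it. They do not replace the armband and recalls, because they cover parent-estimated sedentary time, eating style, feeding practices and the home food environment. They are nonetheless unaffected.

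**The exposure figure overstates the dilution.** Section 6.1.1 allows up to 3 months to reach the TSH range and a further 3 months for effects to appear. A few days on drug after 6 months of placebo may change behaviour very little. This stands, and is why 20–24% is treated as near a ceiling.

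**The key contrasts are before-versus-after.** Sections 6.1.1 and 6.1.2 rest on model-based changes, not month 12 alone. True, but the month-12 record is also Group 1's last before its own treatment, so a model using it carries the same days.

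**Month 18.** A reader might infer that drug stops before the last armband week, because Section 9.4.2 says "thyroid hormone replacement will be discontinued". That sentence refers to completion of the study, and the armband and recalls are themselves study procedures. The order is not stated.

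**Masking.** Families may realise that all children now receive levothyroxine, but they learn their arm only at the end (Section 9.1.3). The documents give no basis for a differential effect.

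**Conclusion.** The concern holds for two instruments at one time point. As scheduled, the month-12 armband record and diet recalls follow the visit at which Group 1 is given levothyroxine, with no safeguard, so the placebo-controlled comparison on these measures may be partly diluted toward no difference.

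For the armband, the dilution is at most about 20–24%. This assumes dosing from the visit, 4–5 half-lives in 6 weeks, and an effect that tracks exposure. It is less if the effect lags, and zero if dosing starts after the week. The recalls cannot be bounded. The comparison is weakened, not destroyed.

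The primary endpoint (non-HDL-C), DXA, BMI-Z, quality of life, body image, ASAQ, CEBQ, CFQ and HFI are unaffected. This is an inexpensive improvement to a secondary aim and does not threaten the trial's main result.

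**What to change.** - **Visit #3:** collect the 7-day armband record and all three recalls in the 7 days before the visit. Mail the armband and diary with the HFI, which already goes out beforehand, and collect them at the visit.
- **Visit #4:** do the same, so that months 12 and 18 match. This also removes the ambiguity about when drug stops.
- **Visit #2:** leave collection after the visit. Subjects recruited from IRB #9233 give written consent for the whole study only at that visit (Section 9.6), so moving these procedures earlier would place them before consent.
- **Recall window and dates:** state a recall window for each visit. Record the first-dose date against the armband and recall dates, so that any on-drug days in the month-6 values can be identified.
- **Text to amend:** Table 1; the Visit #3 and #4 paragraphs of Section 3.1.3; Section 4.3.1; the armband and recall entries in Section 5.1; and the Visit #3 and #4 payment wording in Section 9.7, where the last $25 depends on post-visit procedures.

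Only the measurement moves; treatment timing is unchanged. The cost is a small amendment and postage. Some armbands may be lost or come back unworn. Collection will fall after the visit at months 0 and 6 and before it at months 12 and 18, but equally in both arms.

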3.2 Allocation to Treatment Groups and Blinding

Randomization and allocation concealment: Children will be randomized to two groups. Both will be observed for 6 months. One will be switched to the intervention at 6 months, and continued thereafter. The other will be switched to placebo at 6 months and to the intervention at 12 months. Randomization will be performed centrally by the project statisticians and implemented using opaque sealed envelopes to ensure allocation concealment. Balance between treatment arms will be maintained by use of randomly permuted blocks with unequal block sizes and with stratification by patient gender (two

strata, male and female and age (two strata, ages 8-14 and ages 14-20). After envelopes are opened, treatment assignment will be blinded to the subjects (and their parents).

3.3 Study Duration, Enrollment and Number of Sites

3.3.1 Duration of Study Participation

The total study duration per subject will be between 6 to 18 months.

3.3.2 Total Number of Study Sites/Total Number of Subjects Projected

The study will be conducted at 2 study sites, The Children's Hospital of Philadelphia and Children's National Medical Center. Interim blood draws may take place at satellite Children's Hospital of Philadelphia and Children's National Medical Center sites, if it is more convenient for the family.

It is expected that approximately 29 subjects will be enrolled to yield 20 study completers.

3.4 Study Population

3.4.1 Inclusion Criteria

Inclusion Criteria

1. Males and females, ages 8 – 20 years
2. Diagnosis of Down syndrome
3. Subclinical hypothyroidism: TSH level between 5 – 10 mIU/L, normal T4
4. Parental/guardian permission (informed consent) and if appropriate, child assent
5. Females who are ≥ 11 years of age or who are menarchal must have a negative urine/serum pregnancy test
6. Committed to adherence to levothyroxine treatment and study completion

